#### 7.6 Multisite Studies

This study is conducted in nine sites in the Pelvic Floor Disorders Network. For this multisite study, randomization of study participants was stratified within site. Consequently, for all model-based primary and secondary analyses, site will be included as a fixed effect in the models.

Pooling of sites is defined as grouping the subjects from one or more sites together and considering these subjects as representing a single site for the purpose of summary and analysis. The purpose of pooling is to ensure that each site contains a sufficient number of subjects for sample size requirements of statistical analysis methods that consider site as a factor.

For all statistical analyses, sites with fewer than 25 randomized patients will be pooled based on geographical location. Specifically, UCSD (n=17) and sub-site Kaiser-Downey (n=11) will be pooled with Kaiser- San Diego (n=61), New Mexico (n=1) will be pooled with UTSW (N=26), and Cleveland Clinic (n=3) will be pooled with University of Pittsburg (N=25), resulting in 7 pooled sites.

As a supplemental analysis associated with the primary outcome, we will examine descriptively whether the treatment effect varies across pooled sites; however, no other analyses will assess site differences in treatment effect because sample sizes are inadequate to support evaluation of site-level effects.

## 7.7 Multiple Comparisons and Multiplicity

There are 3 formal primary hypothesis tests and 1 formal step-down test for this study, for the primary outcome of time to treatment failure. The overall Type-1 error (alpha) is maintained at 0.05 by distributing the alpha among the 3 hypotheses as follows:

- H1: transvaginal mesh is noninferior to mesh augmented sacral colpopexy [spend alpha of **0.03** using a one-sided noninferiority test and **an upper bound 1-sided 97% CI**, which is equivalent to the upper bound of a 2-sided 94% CI.]
- H1a (tested only if H1 null hypothesis of inferiority is rejected): transvaginal mesh is superior to mesh augmented sacral colpopexy [spend alpha of **0.03** using a two-sided test of superiority and a **97% CI**]
- H2: mesh augmented sacral colpopexy is superior to native tissue repair [spend alpha of 0.01 using a two-sided test of superiority and a 99% CI]
- H3: transvaginal mesh repair is superior to native tissue repair [spend alpha of 0.01 using a two-sided test of superiority and a 99% CI]

All statistical tests for secondary, and exploratory analyses will be conducted at a 5% type I error rate (two-sided) and no adjustments for multiplicity will be made. P-values and confidence intervals are provided for descriptive purposes only and are not to be evaluated relative to statistical significance.

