#### 6 SAMPLE SIZE DETERMINATION

Sample size calculations were generated under the assumptions that the three study arms are 1) mesh augmented sacral colpopexy, 2) transvaginal mesh repair, and 3) native tissue repair for vault prolapse. Further assumption was that the study would have an overall Type I error rate of 0.05, that a randomization ratio of 1:1:1 is preferred for feasibility reasons, and that the Type I error (alpha) would be distributed among the 3 following three hypotheses related to the 3 treatment arms in a way that optimizes sample size and at the same time is scientifically defensible:

• H1: transvaginal mesh is noninferior to mesh augmented sacral colpopexy [spend alpha of 0.03 using a one-sided noninferiority test]

• H2: mesh augmented sacral colpopexy is superior to native tissue repair [spend alpha of 0.01 using a two-sided test of superiority]

• H3: transvaginal mesh repair is superior to native tissue repair [spend alpha of 0.01 using a twosided test of superiority]

The sample size estimates also assume that the primary analyses for each of the three hypothesis tests will be based on a survival analysis model with a 2-year recruitment period and a 3-year follow-up period after the last participant is randomized and that loss to follow-up on each arm will be no more than 5% per year, that the 2-year success rates for mesh-augmented sacral colpopexy and transvaginal mesh repair will be 80% and that the 2-year success rate for native tissue will be 60%. These 2-year success rates represent hazards of 0.1116 and 0.2554, respectively, under the assumption that the failures follow an exponential survival model. The non-inferiority margin was selected to show that transvaginal mesh success rate at 2 years is no worse than a 15% difference from sacral colpopexy, or 65%. This success rate represents a hazard of 0.2154 and the noninferiority margin corresponds to a hazard ratio of 1.93.

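### H2 and H3 are each held at a fixed two-sided 0.01; a Holm step within the same joint 0.02 would be more powerful with the familywise error still within 0.05

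*SAP*

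**What the plan says.** SAP 7.7 sets out the scheme: "There are 3 formal primary hypothesis tests and 1 formal step-down test for this study". On the error rate it says: "The overall Type-1 error (alpha) is maintained at 0.05 by distributing the alpha among the 3 hypotheses as follows". The shares are:

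- H1, non-inferiority of transvaginal mesh (TVM) to sacral colpopexy (SC): "spend alpha of 0.03 using a one-sided noninferiority test" (SAP 6, repeated in 7.7).
- H2: "H2: mesh augmented sacral colpopexy is superior to native tissue repair [spend alpha of 0.01 using a two-sided test of superiority", with a 99% CI.
- H3: "H3: transvaginal mesh repair is superior to native tissue repair [spend alpha of 0.01 using a two-sided test of superiority", with a 99% CI.

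The instruction in SAP 7.7 for each of H2 and H3 is thus to "spend alpha of 0.01 using a two-sided test of superiority and a 99% CI". The one step-down runs from H1 to H1a, superiority of TVM to SC. Protocol M.1 and SAP 6 give the same shares, and SAP 9.4.2 repeats that both superiority tests against native tissue (NT) are judged at two-sided 0.01. Neither document lets a rejected H2 or H3 release its alpha to the other.

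SAP 6 and Protocol M.1 state 85% power for H1 and more than 93% for each of H2 and H3 with 121 per arm. They name H1 as the test that determines the sample size.

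**The concern.** H2 and H3 together hold 0.02, divided equally and permanently, which is a plain Bonferroni split of that 0.02. Holm's procedure controls the same familywise error under any correlation and is uniformly more powerful. If the smaller of the two p-values is at or below 0.01, that hypothesis is rejected and the other may be tested at 0.02.

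The trial's stated purpose covers superiority of mesh repair by both the abdominal and the vaginal route, so winning both tests matters. Under the fixed rule, a second comparison with p between 0.01 and 0.02 is declared not significant even though the error budget would allow it to be declared. The plan already uses a stepwise rule for H1a but not here.

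**Working it through.** **Inputs** (SAP 6, Protocol M.1): two-year success 80% for SC and TVM and 60% for NT; exponential hazards 0.1116 and 0.2554; margin HR 1.93; R = 2 years' recruitment; F = 3 years' follow-up after the last randomization; 5% loss per year, taken as η = −ln 0.95 = 0.0513; 121 per arm. On allocation the plan says "randomization ratio of 1:1:1 is preferred for feasibility reasons".

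**Events.** With uniform accrual,

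P(event) = λ/(λ+η) × [1 − (e^(−(λ+η)F) − e^(−(λ+η)(F+R))) / ((λ+η)R)].

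This gives 0.3264 for a mesh arm and 0.5847 for NT. Times 121, that is 39.5 events per mesh arm and 70.8 in NT.

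**The plan's own figures first.**

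- H1: SE = √(2/39.5) = 0.225. Power = Φ(ln 1.93/0.225 − 1.881) = Φ(2.922 − 1.881) = 85.1% (stated 85%).
- H2, H3 at two-sided 0.01: log HR = ln(0.2554/0.1116) = 0.828; SE = √(1/39.5 + 1/70.8) = 0.1986. Power = Φ(4.169 − 2.576) = 94.4%. Freedman's formula gives 93.8%, Lachin-Foulkes 94.3% and Schoenfeld 96.2% (stated: above 93%).
- Alpha: 0.03 + 0.01 + 0.01 = 0.05.

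All of these reproduce.

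**Holm within 0.02.** The H2 and H3 statistics share the NT arm, so they are correlated: 39.5/(39.5 + 70.8) = 0.36. I simulated 4 million draws of the three arms' log hazards.

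| Scenario | Quantity | Fixed 0.01 each | Holm in 0.02 |
|---|---|---|---|
| Original design (2-year accrual, 121 per arm) | Each of H2, H3 | 94.4% | 96.4% |
| | Both | 89.9% | 93.8% |
| | At least one | 99.0% | 99.0% |
| 36-month accrual, TVM 115, others 121 | H2 | 95.9% | 97.4% |
| | H3 | 95.2% | 97.0% |
| | Both | 91.8% | 95.1% |

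The second scenario uses what SAP 6 now says: recruitment extended to 36 months and TVM at about 95% of plan (0.95 × 121 = 115).

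Two checks on the first scenario. Testing one hypothesis outright at 0.02 has power Φ(4.169 − 2.326) = 96.7%, and Holm's 96.4% sits just below that ceiling. By symmetry, the gain for both should be twice the gain per test, and 2 × about 2.0 points agrees with 93.8 − 89.9 = 3.9.

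**Error rates.** With both nulls true, the pair's familywise error is 0.019 under either rule, because Holm's first step is the fixed rule. With H2 truly effective and H3 null, H3's own error is 0.0187 under Holm, against 0.01 under the fixed rule. The pair stays within 0.02, so the total stays within 0.03 + 0.02 = 0.05.

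**If effects are smaller.** The documents do not give this case. Assuming 75% success in both mesh arms, each test goes from 69.0% to 74.0% and both from 53.0% to 62.9%.

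**The case against.** The fixed split is valid, its arithmetic is exact and its stated power is met. The plan powers test by test and sets no joint-power target. H2 and H3 already exceed 93% while H1 has 85%, so Holm adds power where the plan is least short of it. The chance of winning at least one does not change. All of this stands, and it limits the weight of the point.

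The fixed rule also has a presentational merit. Each decision matches its 99% CI, and the planned main figure (SAP 14) shows pairwise tests with intervals. Under Holm, a second-step p between 0.01 and 0.02 would be declared superior while its 99% CI still includes 1.0. That stands as a real but small cost.

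Two stronger readings are tempting:

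- SAP 6 says alpha was distributed "in a way that optimizes sample size and at the same time is scientifically defensible", and a reader might infer that the fixed split fails that aim and wastes participants. The documents do not support this. H1 drives the sample size and keeps its 0.03, so Holm between H2 and H3 leaves 121 per arm unchanged. Saving participants would require moving alpha between H1 and the pair, which is a different proposal.
- A reader might infer that the step is free of any error cost. That is true only familywise. As shown above, one hypothesis's own error can rise to about 0.019 when the other is truly effective.

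**Conclusion.** The point holds as an optional improvement. Holm on H2 and H3 dominates the fixed split at the same familywise error. The gain is about 2 points per test and 3.9 points for both under the original design, and 1.5 to 1.8 points per test and 3.3 for both under the extended recruitment. The chance of missing at least one of the two falls from 10.1% to 6.2% in the first case and from 8.2% to 4.9% in the second.

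These figures assume exponential failure, uniform accrual, 5% annual loss and the plan's success rates. They also use a normal approximation to the log hazard ratios in place of the interval-censored model. I give no joint figure with H1, because H1 is analysed per protocol and H2 and H3 in the MITT-narrow population (SAP 5).

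Timing limits what can be done now. SAP Version 2 (section 12) already reports events by arm after year 3 and a proportional-hazards p-value. Relaxing the alpha rule after that point cannot count as pre-specified.

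**What to change.** Before unmasking, replace the two fixed levels with one rule: order the H2 and H3 p-values, test the smaller at two-sided 0.01 and, only if it is rejected, test the other at two-sided 0.02. Leave H1 and H1a at 0.03.

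Make the same change in Protocol M.1 and in SAP 6, 7.7 and 9.4.2; altering 7.7 alone would put the SAP at odds with the protocol and with itself. State that the 99% CIs are reported for estimation, and show a 98% CI beside the 99% one for whichever hypothesis is tested second at 0.02, so that the reader sees an interval that matches the decision.

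The cost is a protocol and SAP wording change, one extra interval and the higher single-hypothesis error noted above. It needs no additional participants or data.

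If unmasking has already happened, keep the fixed 0.01 rule as confirmatory and label any Holm result post hoc. The within-pair step can then be written into the next plan with this three-arm structure.

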## 7.8 Assessment Windows

Ideally, the time from randomization to surgery will be no longer than 6 weeks (42 days). If more than 6 weeks transpires between randomization and surgery, a protocol deviation will be completed. Similarly, the time from consent to surgery should be no longer than 4 months. If more than 4 months transpires between randomization and surgery, a protocol deviation will be completed. Regardless of timing, screening and baseline assessments were not repeated.

If surgery is not scheduled within 6 months after randomization due to patient-specific reasons unrelated to the masked treatment assignment, the patient may be discontinued from the trial.

The 6-week post-op visit had a -1 week, +2 week visit window. All other visits were completed at 6month intervals following the surgery with a  $\pm$  six-week window around the visit. Coordinators attempted to complete all follow-up visits, even if they couldn't be completed within window. For both primary and secondary analysis, decisions about how to treat out-of-window visits will be made during the masked data review prior to unmasking data.

## 8 STUDY SUBJECT CHARACTERIZATION

#### 8.1 Participant Disposition

Participant eligibility status will be summarized and listed by study arm and overall disposition of study participants will be described using a standard Consort diagram. The number of subjects randomized; completing or discontinuing from study therapy; completing each 6-month follow-up visit will be summarized by study arm. Reasons for study treatment discontinuation and study withdrawal will be listed.

#### 8.2 Study Treatment Exposure And Compliance

Because of the surgical nature of the intervention, treatment exposure and compliance are not anticipated to be an issue for this study.

#### 8.3 Protocol Deviations

Protocol deviations are identified via automated checks of the clinical database and reported by site study coordinators in the study data management system. Protocol deviations will be listed by site with information such as type of deviation, time of occurrence, and reason. Incidence rate of protocol deviations will also be summarized overall and for each protocol deviation category by site.

## 8.4 Demographic and Baseline Characteristics

Demographic and baseline clinical characteristics for the study participants will be summarized by study arm using the general analysis rules describe above. Variables of interest include age (years), parity, gravidity, race and ethnicity, marital status, education level (classified as binary variable as having some college or greater or no college education), health insurance status (private only, Medicare/Medicaid only, combination of both), smoking status (never, previous, current), prior prolapse surgery, BMI, and baseline levels of all QOL measures. Treatment groups will not be compared statistically

## 9 EFFICACY ANALYSES

#### **9.1** Overview of Efficacy Analyses Methods

All analyses of the primary efficacy outcome will be performed using populations as specified in Section 5. Analyses of all secondary efficacy outcomes will be performed using the MITT population unless otherwise specified (see section 5, analysis populations). All efficacy variables will be listed by subject within study center and assessment time. The data will be summarized by treatment group. Additional details are provided in the specific sections below.

#### 9.2 Assessment of Non-Inferiority and superiority of TVM to SC

Non-inferiority of TVM to SC will be assessed only for the primary outcome of time to treatment failure. All secondary and exploratory assessments will be evaluated descriptively with a standard 90% confidence interval.

For the primary outcome, non-inferiority is to be assessed using a 1-sided p=0.03 test of the hazard ratio relative to the 1.93 non-inferiority margin. This will be evaluated via a p-value for the 1-sided test that the TVM to SC hazard ratio is not more than 1.93, corresponding to the upper bound of a 2-sided 94% CI being less than the non-inferiority margin of 1.93. The purpose of the non-inferiority test is to assess if we are 97% confident that the TVM hazard is not more (larger) than SC hazard by an amount of 1.93. If the upper bound of the CI is less than 1.93, (corresponding to the 1-sided p-value < 0.03): then the null hypothesis is rejected, and non-inferiority is assumed. The lower bound of the CI is not evaluated.

If non-inferiority is assumed, then a further step-down test of superiority of TVM to SC is completed by a 2-sided test with p=0.03, corresponding to a 2-sided 97% confidence interval. Note that while non-inferiority is evaluated with a protocol-specified 1-sided test, superiority is evaluated with a 2-sided test.

#### **9.3** Efficacy Variables **Timepoint(s)** Variable Type Definition CRF Source **Primary Efficacy Outcome** 6 months through 60 Time to surgical CRF-13, Continuous Among subjects who experience a surgical failure (see months CRF-12, definition below) starting at the 6 month post-operative failure CRFvisit through their last attended ASPIRE visit, the time to surgical failure is defined as the number of months (i.e. 14/37 months as intended by the visit schedule) from the surgical intervention to first post-operative visit with surgical failure. Surgical failure is defined at each attended post-operative visit if any ONE of the following criteria is met: Retreatment failure is defined as retreatment for \_ prolapse via additional surgery or pessary as reported on coordinator follow-up CRF-13 Anatomic failure is defined as any prolapse beyond the hymen (i.e. POPQ points Ba, Bp, or C > 0.0 cm) as reported on the evaluator (blinded) follow-up CRF-12 during POPQ examination Symptomatic failure is defined as experiencing bothersome vaginal bulge symptoms as reported on CRF-14/37. Bothersome vaginal bulge symptoms are defined as a positive response to Question 3 Do you usually have a bulge or something falling out that you can see or feel in your vaginal area? AND any degree

of bother greater than "Not at all" (i.e. "Somewhat",
"Moderately", or "Quite a bit")
Participants not meeting the criteria for surgical failure at the attended post-operative visit will be considered not a surgical failure, regardless of missingness of the 3 components of the surgical outcome (i.e. retreatment failure, anatomic failure, and symptomatic failure).
The time to surgical failure will be missing for all participants who are considered not a surgical failure at each of the attended post-operative visits 6 months through their last attended ASPIRE visit scheduled in 6- month intervals up to 60 months.
Note that since ASPIRE followed participants until the last participant completed their 36 month visit, ASPIRE study completers have a varying amount of follow-up time from 36 to 60 months.
For survival analysis, participants with no failure by their last attended study visit are censored, and with follow-up duration equal to the number of months (i.e. months as intended by the visit schedule) corresponding to the last attended visit.
Note that due to COVID, there are more missed visits than would have been expected pre-pandemic, as well as remotely-attended visits with missing POP-Q exams. The calculation of the primary outcome is unchanged.

Secondary Efficacy Outcomes				
Indicator of surgical failure at post- operative visit under the permanent failure state assumption	CRF-13, CRF-12, CRF- 14/37	Binary	1-, 2-, 3- , 4-, 5-years	At each timepoint , surgical failure under the permanent failure state assumption is defined if any one of the three criteria (retreatment, anatomic, or symptomatic) is met at the timepoint's corresponding attended post-operative visit or at any prior attended post-operative visits (i.e. 6- month post-operative visits 6 months up to 60 months):
				Participants not meeting the criteria for surgical failure at the timepoint's corresponding post-operative visit (if attended) and at all prior attended post-operative visits will be considered not a surgical failure, regardless of missingness of the 3 components of the surgical outcome at any of the attended post-operative visits through the timepoint. Participants who discontinued prior to the 6- month post-operative visit will be missing the permanent failure state surgical outcome at all timepoints.
				By this definition, a subject can be defined as a surgical failure at timepoints corresponding to missed post- operative visits or post-operative visits occurring after subject's discontinuation from the study IF the subject had a surgical failure prior to the missed visit or discontinuation.
Initial failure type	CRF-13, CRF-12, CRF- 14/37	Nominal Categorical (4 levels)	1-, 2-, 3- , 4-, 5-years	At each timepoint, subjects who experience a surgical failure under the permanent failure state assumption, failure type will be defined for the initially occurring surgical failure.
				Each initial surgical failure will be categorized into the following 4 types: "retreatment failure", "anatomic

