## 7.3 Handling of Dropouts and Missing Data

Standard procedures will be used to ensure that data are as complete and accurate as possible. The study was designed to obtain as much follow-up data as possible on all randomized subjects. In analyses, a full accounting will be made for all data items. Generally, missing data will initially be treated as randomly missing (either missing at random (MAR) or missing completely at random (MCAR) as appropriate for the analytic approach) with no data imputation. Sensitivity analyses addressing the impact of missing data will be specifically specified.

**Impact of COVID 19** Some of the follow-up period of this study coincided with the COVID pandemic (March 2020 – July 2022). At varying times across sites during the pandemic, patients were unable or unwilling to attend in-person visits, or clinic site personnel were unable to conduct inpatient visits. Accommodations were made allowing for remote phone contact visits rather than inperson visits. All such visits were noted as a COVID-related protocol violation. As a result, there are more study visits missed than ordinarily expected in pre-pandemic, and also a percentage of study visits done remotely in which the subjective assessments of the primary outcome were recorded, but the anatomical POP\_Q exam of prolapse was not able to be performed. An effort was made by all sites to have participants complete a final POP-Q exam prior to study completion whenever possible. Assessments of the impact of missingness from the COVID pandemic on the primary outcome and sensitivity analyses are specified in applicable sections below.

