#### Pelvic Floor Disorder

				failure", "symptomatic failure", and "anatomic and symptomatic failure" where retreatment failure corresponds to retreatment for prolapse, symptomatic failure corresponds to bothersome vaginal bulge symptoms, and anatomic failure corresponds to prolapse beyond the hymen as described in the surgical failure under the permanent failure state assumption definition above. Retreatment failure type is prioritized above the anatomic and/or symptomatic failure types.
Indicator of surgical failure at post- operative visit under the transient failure state assumption	CRF-13, CRF-12, CRF- 14/37	Binary	1-, 2-, 3- , 4-, 5-years	At each timepoint, surgical failure under the transient failure state assumption is defined if any one of the three criteria (retreatment failure at that visit or any prior visit, anatomic failure at that visit, or symptomatic failure at that visit) is met at that visit.
				Participants not meeting the criteria for surgical failure at the timepoint will be considered not a surgical failure, regardless of missingness of the 3 components of the surgical outcome at the timepoint's corresponding attended post-operative visit.
				Participants who have discontinued from the study by timepoint's corresponding post-operative visit will be missing the transient failure state surgical outcome at the timepoint.
				Participants who missed the post-operative visit corresponding to the timepoint without a retreatment failure at any prior attended post-operative visit will also be missing the transient failure state surgical outcome at the timepoint.

				By this definition, a subject can be defined as a surgical failure at timepoints where the corresponding post- operative visit is missed IF the subject is still participating in the study and had a surgical failure due to retreatment failure at any prior attended post-operative visit (i.e. post- operative visits 6 months up to 60 months).
At-visit failure type	CRF-13, CRF-12, CRF- 14/37	Nominal Categorical (4 levels)	1-, 2-, 3- , 4-, 5-years	At each timepoint, subjects who experience a surgical failure under the transient failure state assumption, failure type will be defined for the surgical failure occurring at the timepoint.

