# 9.4.2 Primary Efficacy Analysis: Model-Based Survival Analysis

This model-based approach will serve as the primary analytic method for testing the comparative efficacy of the three strategies for uterovaginal prolapse as it can control for study design and potentially confounding variables. To appropriately account for the interval censored and right censored nature of the primary outcome data, and potential violation of the proportional hazards assumption across the entire follow-up time, while controlling for study design and potentially confounding variables in assessing intervention effects, a piecewise exponential (PWE) survival model will be employed. The PWE survival model is a model in which the time scale is divided into *K* periods and the underlying hazard function, h(t), is assumed to be constant within each period such that  $h(t) = \lambda_k \exp(\beta \mathbf{X})$ , where  $\lambda_k$  is the hazard function for period *k*, and **X** is a matrix of explanatory

variables with vector  $\beta$  coefficients (Breslow 1974). This piecewise approach effectively eliminates the need to specify the distribution of the hazard function and satisfies the proportional hazards assumption if the underlying hazard is constant within each period.

Among subjects who experience a surgical failure, the time to surgical failure (primary outcome) will be interval censored (i.e. lower bound, upper bound where both bounds are non-missing and lower bound < upper bound). Subjects who do not experience a surgical failure will be right censored (i.e. non-missing lower bound and missing upper bound) at their last attended visit. Specifically, the censoring interval for implementation in interval censored analysis will be defined as follows:

- lower bound = number of months (i.e. months as intended the by visit schedule) from the surgical intervention to the *last attended visit where the subject was considered to be not a surgical failure* across all post-operative visits starting at the 6 month visit. As such, subjects who were surgical failures at the 6-month post-operative visit will have a lower bound of 1.5 months corresponding to the 6-week post-operative visit. Based on this definition, the lower bound for the primary endpoint of 3 to a maximum of 5 years can take any of the following values 1.5, 6, 12, 18, 24, 30, 36, 42, 48, 54, or 60 months.

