## Sensitivity Analysis evaluating impact of missed visits due to COVID pandemic

A sensitivity analysis of the primary outcome through the primary endpoint of 3 to a maximum of 5 years on the primary analysis population will be conducted via the previously described PWE survival model, with an additional covariate controlling for the year of the participant enrollment, and also testing for the interaction between enrollment cohort and overall treatment effect. Since enrollment was over 3 years, and the last patients were enrolled in 2018, the year 1 cohort had impact of 2020 and 2021 pandemic at the end of their follow-up, and the last participants enrolled had this impact in earlier years of their enrollment.

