### Post-hoc Sensitivity Analysis excluding data after the 3 year visit

A sensitivity analysis of the primary outcome through the primary endpoint excluding data after the 3 year visit on the primary analysis population will be conducted to evaluate the proportional hazards assumption during the first 3 years. Failure probability, hazard rate, and hazard ratio estimates and their corresponding confidence intervals and p-values are from an interval-censored proportional hazard model with an assumed underlying piecewise exponential hazard with three constant-hazard periods: [0, 12], (12, 24], (24, 36]. Excluding follow-up years 4 and 5 removed 14 events (2 events in NTR, 5 events in SC, and 7 events in TVM). The proportional hazards assumption is not violated in the MITT population (p=0.155).

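### Visits without a POP-Q count as free of failure in the primary outcome, and no planned analysis tests that rule

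*SAP*

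**What the plan says.** SAP section 9.3 defines failure at each attended visit from three components: retreatment, prolapse beyond the hymen on POP-Q, and bothersome bulge. A woman who meets none of them "will be considered not a surgical failure, regardless of missingness of the 3 components of the surgical outcome". The same entry notes missed visits and "remotely-attended visits with missing POP-Q exams. The calculation of the primary outcome is unchanged".

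SAP section 9.4.2 sets the lower bound of the censoring interval at the "last attended visit where the subject was considered to be not a surgical failure". Women who never fail are censored there. No POP-Q is required for a visit to serve this purpose.

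The by-visit indicator for transient failure repeats the rule: "Participants not meeting the criteria for surgical failure at the timepoint will be considered not a surgical failure", again whatever is missing.

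SAP section 7.3 explains that some visits between March 2020 and July 2022 were remote, with symptoms recorded but no POP-Q. It says: "Assessments of the impact of missingness from the COVID pandemic on the primary outcome and sensitivity analyses are specified in applicable sections below". It also records a mitigation: "An effort was made by all sites to have participants complete a final POP-Q exam prior to study completion whenever possible".

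The one COVID analysis in section 9.4.3 refits the primary model "with an additional covariate controlling for the year of the participant enrollment" and tests an enrolment cohort by treatment interaction. Section 12 adds a post-hoc refit "excluding data after the 3 year visit on the primary analysis population".

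**The concern.** A missed visit cannot serve as evidence of no failure, but an attended visit without an examination can. Coding an absent POP-Q as negative is a single favourable imputation. Section 7.3, by contrast, says missing data will generally be handled as randomly missing without imputation. The affected component is central: the primary aims concern anatomic correction, and the masking argument in section 4.4.1 rests on a masked examiner who is absent from a remote visit.

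The damage is bounded. Bulge symptoms or retreatment reported remotely still count, so only anatomic-only failures can be hidden. A persistent one is dated too late if a later POP-Q finds it, and lost if no POP-Q follows. Failure probabilities are pulled down. The TVM:SC hazard ratio moves only if the hidden failures are not shared evenly between the arms, and it can then move either way against the 1.93 margin.

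**Working it through.** **The plan's own figures.** Margin: ln(0.65)/ln(0.80) = 1.9305. SC hazard: -ln(0.80)/2 = 0.1116 per year. With 5% annual loss and 2 years of accrual plus 3 years of follow-up, P(event) = 0.326, so 242 × 0.3264 = 79.0 events. Power = Φ(ln 1.93 × √(79.0/4) - 1.881) = Φ(1.04) = 0.851, against the stated 85%.

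**Exposure.** The protocol addendum puts the first subject at six years in March 2022, so the first surgery was about March 2016. SAP section 4.4.2 gives the last as 10 June 2019. Assume surgeries were even over these 3.27 years.
- A 36-month visit falls in the COVID period if surgery was after March 2017: 2.27/3.27 = 69%.
- At 6, 12, 18, 24, 30 and 36 months the shares are 0, 8.5, 23.7, 39.0, 54.2 and 69.5%, a mean of 194.9/6 = 32.5%. The 3-year refit therefore keeps about a third of its visits in the period.
- At 48, 54 and 60 months the share is 100%. Over all scheduled 6- to 60-month visits it is about 50-51%.
- Every completer's final visit lies between March 2021 and June 2022, so all are in the period.
- By enrolment cohort (first year, second year, remainder) the shares are about 35, 51 and 69%. No cohort is free of COVID visits to serve as a reference for the enrolment-year analysis.

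**Mechanism.** Take a woman with a negative POP-Q at 18 months who develops persistent, symptom-free prolapse before 24 months, has remote visits at 24 and 30, and a POP-Q at 36. With every POP-Q done, her interval is (18, 24]. Under the SAP it is (30, 36]. If the remote visits are treated as missed it is (18, 36], which is wide but contains the truth. If the 36-month visit is also remote and is her last, the SAP censors her as failure-free at 36, whereas treat-as-missed censors her at 18.

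**Size.** Simulation of 250,000 women per arm: the calendar above, SC hazard 0.1116, TVM hazard 1.93 times that, 5% loss per year, and the interval-censored piecewise exponential model with cuts at 12, 24, 36 and 48 months. The SC hazard error comes from a one-arm interval-censored exponential fit. Type I error is a normal approximation at 118 per arm, one-sided 0.03.

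These inputs are assumptions, because the documents give no values: 20-50% of COVID-era visits and 10-50% of final visits lack a POP-Q; 20% of failures that are not anatomic-only are retreatment; failures persist.

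| Rule; anatomic-only share SC/TVM | SC hazard | TVM:SC HR | Type I error |
|---|---|---|---|
| All POP-Qs done | reference | 1.934 | 0.029 |
| SAP; 40/40 and 60/60 | 0.7-6.6% low | 1.93 | 0.029-0.030 |
| SAP; 40/80 | not tabulated | 1.85-1.92 | 0.032-0.048 |
| SAP; 80/40 | not tabulated | 1.95-2.02 | 0.018-0.027 |
| Treat as missed; all of these | 0 to 1.1% high | 1.92-1.95 | 0.027-0.031 |

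With equal shares and 80-90% of final visits examined, the first SAP range narrows to 0.7-3.4% low. If half of anatomic-only failures show at one visit only (equal shares), the SAP rule is 2.2-10.5% low and treat-as-missed 1.4-5.2% low.

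A separate simulation (100,000 per arm; 20-60% of COVID-period visits remote, 20-80% anatomic-only, 0-90% final POP-Q) gave SC 3-year failure of 26.9-28.4% under the SAP rule. The true value is 1 - exp(-0.1116 × 3) = 28.5%.

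**By-visit rates at 3 years** (SC, persistent failure, 12-35% of 36-month visits remote): the transient indicator falls from 28.4% to 22.5-27.0%, and the permanent indicator from 29.8% to 28.4-29.6%.

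**The case against.** The rule is disclosed, applied alike in all arms, and follows from a composite in which any one criterion suffices. A plan cannot contain the remote share or the failure mix. The SAP does plan to tabulate failure types by year and completeness by arm (eTables 1A and 1B), to show COVID timing, and to hold a masked review of missed visits and of individual failures. Table shells are in a separate document and may already split out POP-Q completion.

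Half of scheduled visits also overstates exposure, since visits after first failure are irrelevant. Among attended visits up to first failure, about 43% (SC) and 39% (TVM at HR 1.93) fall in the period, and only some were remote. Nothing in the documents suggests an 80/40 split between two mesh arms. Protocol section B.4 says prolapse beyond the hymen correlates highly with symptoms. At a 20% share in both arms, SC 3-year failure is 27.9-28.4% against 28.5%. The 0.048 needs half of final visits unexamined; with 80-90% examined, the 40/80 mix gives 0.032-0.041.

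Much of this stands as a limit on size. It does not remove the gap. The failure-type table counts only detected failures, so it cannot show those the rule hides. Completeness tables describe the problem without re-estimating anything, and the masked review does not change the coding.

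**Conclusion.** The concern holds and is worth fixing. The rule treats an unexamined woman as anatomically intact, and none of the planned or post-hoc analyses recodes such a visit, despite the assurance in section 7.3.

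The bias in failure probabilities is downward and modest: 0.7-6.6% on the SC hazard with persistent failures and equal anatomic-only shares of 40-60%, and up to 10.5% if half of those failures are transient. With equal shares, the non-inferiority comparison is essentially unaffected. It is disturbed only if the anatomic-only mix differs markedly between TVM and SC, and the direction then depends on which arm has more.

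This does not show the non-inferiority test to be invalid. Every size quoted rests on assumed remote, final-visit and anatomic-only shares. Error rates were worked out for H1 only; H1a, H2 and H3 were not examined.

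**What to change.** 1. Add to SAP section 9.4.3 a refit of the primary piecewise exponential model, for all four hypotheses, in which every visit without a POP-Q is treated as missed for both the lower and the upper bound. Retreatment still counts.
2. Have eTable 1A show POP-Q done, attended without POP-Q, and missed, by arm and visit, with the final visit shown separately.
3. Apply the same rule to the transient indicator, dropping visits without a POP-Q whether the other components are positive or negative, except for retreatment.
4. For the permanent indicator, take the year 1-3 probabilities from the refitted model. Its denominator retains earlier failures, so dropping visits there would give 32.3-37.7% against 29.8%.

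Do not move the lower bound alone, or blank only the negative visits. Bulge failures found remotely would still count while negative remote visits would not, and the SC hazard would be overstated by up to 6% at a 40% anatomic-only share and 8% at 20%.

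The cost is one rerun on re-derived bounds and one table. The sensitivity analysis has about 0.5-6% fewer events and slightly wider intervals, and it sets aside bulge failures reported without an examination. It only partly repairs failures that appear at one remote visit and resolve. SAP Version 2 already reports events by arm, so the analysis should be labelled post hoc. SAP section 2 allows added exploratory analyses without an amendment, but a written rule is preferable for the primary outcome.
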